### 3.3 SAFETY ASSESSMENT

Safety monitoring will include:

- 1) Local and systemic events for 7 days following each dose as noted in the Participant Diary
- 2) All adverse events including SAEs, AESIs, SUSARs, UADEs, and other unexpected AEs for the duration of the study.

All subjects will be followed through Week 78 under Amendment 5.0, or up to 100 weeks if beyond Week 78 at the time of Amendment 5.0.

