## SUMMARY OF CHANGES

The following are a list of protocol changes from Version 3.0 dated 26 March 2019 to Version 5.0 dated 19 December 2019. Protocol Amendment 4.0 was prepared by the Sponsor, but was not distributed to sites nor submitted to the FDA. Since Version 4.0 was finalized internally and never implemented, it was not be incorporated into this protocol. This amendment notes changes since Version 3.0 only. Changes not listed in this summary are administrative and do not affect the safety or subjects, trial scope, or scientific quality of the protocol.

1. Protocol HPV-201 has been amended to end at Week 78 instead of Week 100. This change is prompted by a decision to focus on a 4-dose regimen for the development of VGX-3100 for vulvar HSIL, with the potential for a booster dose at Week 52. A 6th dose will not be pursued, therefore optional dose 6 and the corresponding visits at Weeks 96 and 100 have been removed. Subjects who were already beyond Week 78 or who had received dose 6 prior to Amendment 5.0, will complete the study at the next scheduled timepoint following consent on the associated IRB-approved informed consent form and data collected will be analysed. Cervical colposcopy, scheduled for Week 96, will be done at Week 74 or discharge, for subjects who end the study at Week 78. The socio-behavioral evaluation scheduled for Week 100, will be done at the subjects final discharge visit.
2. The estimated number of Study Centers and Countries/Regions has been updated to more accurately reflect site participation.
3. Secondary endpoint #1b (Protocol Synopsis and Section 2.2) was updated to include adverse events of special interest (AESIs) which is included amongst the adverse events evaluated for secondary objective #1, but was inadvertently not mentioned.
4. Secondary Endpoint #6 was modified to remove Week 74 and 96 from the secondary endpoint analysis since these timepoints are evaluated in Exploratory Endpoint #1.
5. Secondary Endpoints #7a and #7b have been moved to Exploratory Endpoint #8a and #8b.
6. Secondary Endpoint #8 and Exploratory Endpoint #9 have been added to evaluate the efficacy of VGX-3100 treatment alone or in combination with imiquimod, on HPV-16/18 positive vulvar HSIL at Week 48, as HPV-16/18 associated HSIL is considered a significantly higher risk for vulvar cancer.

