## STUDY SCHEDULE OF EVENTS

**Table 1: Schedule of Events**

Tests	Screen (-10 wk to -1d)	Day 0	8-14 days post dose 1 Phone Call	Week 4 (± 7 days)	8-14 days post dose 2 Phone Call	Week 12 (± 7 days)	Week 15 (± 7 days)	Week 24 (± 7 days)	Week 27 (± 7 days)	Week 38 (± 7 days) Phone Call	Week 48 (± 7 days)	Week 52 (± 14 days)	Week 74 (± 14 days)	*Week 78 (± 14 days) Phone Call	Week 96 (± 14 days)	Week 100 (± 14 days)
Informed consent	X															
Medical History/Demographics	X															
Medications (prior/concomitant)	X	X	X	X	X	X	X	X	X	X	X	X	X	X	X	X
Socio-behavioral assessment a	X										X					X a
Inclusion/Exclusion criteria	X	X														
Randomization		X														
Physical exam (PE)/assessment b	X	X		X		X		X	X		X	X	X	X b	X	X
Vital signs	X c	X		X		X		X	X		X	X	X	X c	X	X
Screening safety (12 lead ECG, labs) d	X															
Pregnancy Testing e	X	X		X		X		X	X		X	X	X	X	X	X
HIV Ab by ELISA	X															
Blood immunologic samples	X f	X f					X f		X g		X f		X f		X f	
OP rinse, vaginal, and intra-anal swabs		X							X		X		X		X	
Vulvar swabs		X		X		X			X		X		X		X	
Cervical colposcopy h		X											X h		X h	
Cervical cytology, ThinPrep® i		X				X					X				X	
Vulvoscopy j	X	X		X		X			X		X		X		X	
Vulvar lesion standardized photography k	X	X		X		X			X		X		X		X	
Biopsy l	X										X		X		X	
Vulvar HPV genotyping m	X										X		X		X	
Inject VGX-3100 +EP n		X		X		X		X				X n		X n		
Post treatment reaction assessment		X		X		X		X				X n		X n		
Dispense imiquimod + distribute imiquimod dosing log o		X		X		X										
Review imiquimod dosing log and usage				X		X		X								
Distribute Participant Diary (PD)		X		X		X		X				X n		X n		
Review PD p			X		X		X		X				X		X	
Adverse Events	X	X	X	X	X	X	X	X	X	X	X	X	X	X	X	X
Patient Reported Outcomes (PROs) q		X	X	X	X	X	X	X	X		X	X	X		X	X

\*Under Protocol Amendment 5.0, subjects will complete the study at Week 78, which may be completed by phone. Subjects who are beyond Week 78 at the time of IRB approval of the amendment, will complete the study at their next scheduled visit.

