## 2.2 SECONDARY OBJECTIVES AND ASSOCIATED ENDPOINTS

Secondary Objectives	Associated Secondary Endpoints
1. Evaluate the safety and tolerability of VGX-3100 delivered IM followed by EP with CELLECTRA™ 2000, alone or in combination with imiquimod	1a. Local and systemic events for 7 days following each dose as noted in the Participant Diary. 1b. All adverse events including SAEs, AESI's, SUSARs, UADEs, and other unexpected AEs for the duration of the study (through Week 100 visit) 
2. Determine the efficacy of four doses of VGX-3100, alone or in combination with imiquimod, as measured by histologic regression of vulvar HSIL	2. Proportion of subjects with no evidence of vulvar HSIL  on histology (i.e. biopsies or excisional treatment) at Week 48 visit
3. Determine the efficacy of four doses of VGX-3100, alone or in combination with imiquimod, as measured by virologic clearance of HPV-16/18 in vulvar tissue	3. Proportion of subjects with no evidence of HPV-16/18  in vulvar tissue samples at Week 48 visit
4. Determine the efficacy of VGX-3100 , alone or in combination with imiquimod, as measured by histologic regression of vulvar HSIL to normal tissue	4. Proportion of subjects with no evidence of vulvar HSIL, no evidence of vulvar LSIL (VIN1), and no evidence of condyloma on histology (i.e. biopsies or excisional treatment) at the Week 48 visit
5. Determine the efficacy of four doses of VGX-3100 , alone or in combination with imiquimod, as measured by non-progression of vulvar HSIL to vulvar cancer as determined by histology	5. Proportion of subjects with no progression  of vulvar HSIL to vulvar cancer from baseline to Week 48 visit
6. Determine the efficacy of VGX-3100, alone or in combination with imiquimod, as measured by reduction in the surface area of the qualifying  vulvar lesion(s)	6. Percent reduction in the cumulative surface area of the acetowhite vulvar lesion(s) as determined by the quantitative analysis of standardized pre-biopsy photographic imaging of the qualifying lesion (s) at Week 48 compared to baseline  . Results will be classified as: no clinically significant lesion resolution (reduction in lesion size of 0-25%), partial lesion area resolution (>25% and <100% reduction), and complete lesion resolution (no visible lesion).

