### 8.2 RANDOMIZATION AND BLINDING

Subjects will be randomized two to one, VGX-3100 alone: VGX-3100 in combination with topical imiquimod. Subjects will be randomized in a stratified manner according to (a) recurrent disease at screening (0 vs. 1 or more recurrences), (b) multifocal disease (1 vs. 2 or more lesions at screening), (c) Body Mass Index (BMI) category ( $\leq 25$  vs.  $> 25$  kg/m^2) on Day 0, and (d) age category ( $< 45$  years vs.  $\geq 45$  years) on Day 0. There are no requirements for the number of subjects in each stratum. The study is open-label.

The Version 3.0 protocol amendment halts enrollment of the VGX-3100 with topical imiquimod study group. All subjects who have already been enrolled into the VGX-3100 with imiquimod study group will continue with all study visits per protocol, but no further participants will be enrolled into this group.

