### **8.11 SAFETY ANALYSES**

All AEs will be summarized among the safety population by frequency per treatment arm. These frequencies will be presented overall and separately by dose, and will depict overall, by system organ class and by preferred term, the percentage of subjects affected. Additional frequencies will be presented with respect to maximum severity and to strongest relationship to Study Treatment. Multiple occurrences of the same AE will be counted only once following a worst-case approach with respect to severity and relationship to Study Treatment. All serious AEs will also be summarized as above.

The main summary of safety data will be based on events occurring within 14 days of any dose. For this summary, the frequency of preferred term events will be summarized with percentages and exact Clopper-Pearson 95% confidence intervals. Separate summaries will be based on events occurring within 7 days of any dose and regardless of when they occurred.

Any AEs with a missing or partial onset date will be included in the overall AEs, but not be included within specified day-range summaries. AE duration will be calculated as (Stop Date – Start Date) + 1.

Measurements for vital signs as well as changes from baseline will be summarized with descriptive statistics: mean standard deviation, minimum, median, and maximum values by time point and treatment arm, for the mITT population. Baseline is defined as the last measurement prior to the first treatment administration.

The percentage of subjects with abnormal physical examination findings at each time point will be summarized by treatment study group and by body system, for the mITT population.

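### Two staggered amendments may leave the imiquimod arm observed for longer, and the all-time by-arm AE and SAE percentages in Section 8.11 do not allow for it

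*Protocol*

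**What the plan says.** - **Length of follow-up.** Section 3.3 has subjects "followed through Week 78 under Amendment 5.0, or up to 100 weeks if beyond Week 78 at the time of Amendment 5.0". The note to Table 1 gives the trigger: "Subjects who are beyond Week 78 at the time of IRB approval of the amendment, will complete the study at their next scheduled visit". That visit is Week 96 or Week 100. Section 7.2 collects AEs up to each woman's own final visit.
- **Enrolment by arm.** Section 8.2: "The Version 3.0 protocol amendment halts enrollment of the VGX-3100 with topical imiquimod study group". Women already in that arm continue, "but no further participants will be enrolled into this group". Exclusion criterion 10 (imiquimod allergy) is limited to subjects enrolled before Version 3.0, so the protocol expects VGX-3100-alone enrolment to go on after it.
- **Dates.** The Summary of Changes runs from "Version 3.0 dated 26 March 2019 to Version 5.0 dated 19 December 2019".
- **Analysis.** Section 8.11: "All AEs will be summarized among the safety population by frequency per treatment arm". The main summary covers events within 14 days of any dose. Two separate summaries cover events within 7 days of a dose and events at any time. SAEs are handled in the same way. No common cut-off or observation-time denominator is stated for the all-time summary.
- **Endpoint 1b** (Section 2.2) still reads "other unexpected AEs for the duration of the study (through Week 100 visit", but it carries footnote 4, which says that Amendment 5.0 removes Weeks 96 and 100.

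**The concern.** A percentage of women ever affected rises with time under observation. Under Amendment 5.0 that time depends on when a woman entered, and entry time is not balanced between arms because only one arm closed at Version 3.0. The all-time AE and SAE tables could therefore show somewhat more affected women in the combination arm only because they were watched longer.

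The intensity of observation can differ too. Section 6.2.13 allows a Week 78 ending by phone, without vital signs. Weeks 96 and 100 are in-person visits, and Week 96 includes vulvoscopy and biopsy. For efficacy, Amendment 5.0 did respond: Section 8.9 splits the Week 74 and Week 96 endpoints by number of doses received. Section 8.11 presents AEs by dose, which separates dose-6 events but does not equalise observation time.

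**Working it through.** The protocol states no figure for observation time by arm, so there is none to reproduce.

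**Step 1: who can pass Week 78 before the cut?**
- From 26 March 2019 to 19 December 2019 is 268 days, or 268/7 = 38.3 weeks.
- On 19 December 2019 a woman was beyond Week 78 only if her Day 0 fell before 21 June 2018 (78 weeks earlier).
- A woman enrolled after 26 March 2019 was then at Week 38.3 at most. She could pass Week 78 before the cut only if IRB approval came about 78 − 38.3 = 39.7 weeks or more after 19 December 2019, that is, after about 22 September 2020.

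So VGX-3100-alone women enrolled after Version 3.0 are in practice all capped at Week 78. Among women randomised concurrently before Version 3.0, the cut falls on both arms alike.

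**Step 2: mean planned observation.** Let *a* be the share of pre-Version-3.0 women already beyond Week 78 at the cut (taken as equal in both arms because of randomisation), and *b* the share of the VGX-3100-alone arm enrolled after Version 3.0. Take Week 100 as the end for those beyond Week 78, and ignore withdrawals.

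- Imiquimod arm: 78 + 22*a* weeks
- VGX-3100 alone: 78 + 22*a*(1 − *b*) weeks
- Difference: 22*ab* weeks

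**Step 3: effect on a percentage.** Assume a constant hazard *h* with risk *r* at Week 78, so *h* = −ln(1 − *r*)/78. The risk at Week 100 is 1 − exp(−100*h*): 12.6% for *r* = 10% and 48.1% for *r* = 40%. The by-arm difference is *ab* × (risk at Week 100 − *r*).

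**Step 4: scenarios.** The inputs are assumptions, with 2:1 allocation before Version 3.0, so *k* imiquimod women imply 2*k* concurrent VGX-3100-alone women.

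| Imiquimod women | VGX-3100 alone, total (after V3.0) | *b* | *a* | Difference in weeks | Percentage points, *r* = 10% to 40% |
|---|---|---|---|---|---|
| 12 | 24 (0) | 0 | any | 0 | 0 |
| 8 | 24 (8) | 0.33 | 0.5 | 3.7 | 0.4 to 1.3 |
| 8 | 28 (12) | 0.43 | 0.5 | 4.7 | 0.6 to 1.7 |
| 6 | 30 (18) | 0.60 | 1 | 13.2 | 1.6 to 4.8 |

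The last row is an extreme. *a* = 1 requires that nobody enrolled between 21 June 2018 and Version 3.0, or that IRB approval came about 40 weeks late. If everyone beyond Week 78 ended at Week 96 instead, the factor 22 becomes 18 and that row gives 18 × 0.60 = 10.8 weeks. For scale, one woman in an arm of 12 is 1/12 = 8.3 points.

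**The case against.** The strongest reply has four parts.

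1. **The imbalance is not documented.** The protocol gives no enrolment dates, no counts per arm at Version 3.0 and no IRB approval dates. A reader might infer that the imiquimod arm was in fact followed longer, or that events after Week 78 have no counterpart among VGX-3100-alone women. The documents support neither. The difference is zero if both arms were full at Version 3.0 or if nobody was beyond Week 78 at the cut, and the concurrently randomised VGX-3100-alone women are such counterparts. This part stands, and it makes the point conditional.
2. **The main safety summary is not at issue.** It is limited to 14 days after a dose and does not depend on total follow-up, apart from the optional sixth dose, which adds one window for some earlier women. This stands.
3. **No between-arm safety test is planned.** Each arm is tested separately against 2% in Section 8.9, and safety is descriptive. This stands, but tables laid out by arm will still be read across.
4. **Cut-offs and denominators are SAP matters.** This stands only in part. Section 8.11 itself fixes percentages of subjects affected, at any time, per arm. A separate SAP, not seen here, may already add a cut-off, in which case nothing more is needed.

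Endpoint 1b might also look like a contradiction. It is not: footnote 4 and Section 7.2 already state the final-visit rule.

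**Conclusion.** The point holds conditionally and is minor. If any VGX-3100-alone woman enrolled after Version 3.0, and any earlier woman was beyond Week 78 at IRB approval of Amendment 5.0, mean observation time is longer in the imiquimod arm. The all-time by-arm AE and SAE percentages in Section 8.11 then compare unequal follow-up. The direction is fixed by the design; the size is not. It is 0 to about 13 weeks, or 0 to about 5 percentage points, in the scenarios tried, and about 4 to 5 weeks and under 2 points in the middle ones. These figures rest on assumed arm counts, an assumed share beyond Week 78, a constant hazard, and Version 3.0 taking effect on its date.

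A reader might go further and conclude that the safety comparison as a whole is biased against the combination. The documents do not support that: the main summary is largely untouched, and even the extreme scenario moves a percentage by less than one woman in an arm of 12.

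**What to change.** In Section 8.11, count the all-time by-arm AE and SAE percentages only for events with onset up to Week 78, or up to earlier withdrawal. List later events in a separate table with the number of women followed beyond Week 78 in each arm. Alternatively, report woman-time and events per woman-year by arm beside the crude percentages.

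The cost is a date cut or a denominator in existing tables, plus one more table. No event is lost, and no visit or treatment rule changes. The sponsor holds the enrolment dates; if the imbalance is nil, the added figures will show that. Endpoint 1b needs no more than tidying.

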#### 3.3.1 DATA SAFETY & MONITORING BOARD

An independent Data Safety & Monitoring Board (DSMB) will provide safety oversight. The DSMB will meet quarterly to review safety data and regression/clearance results. The DSMB will be charged with advising the Sponsor if there appears to be a safety issue. No formal interim analysis is planned. The following stopping rules will be applied:

- If at any time during the study one-third (1/3) or more of the subjects experience an Adverse Event of Special Interest verified per protocol definition, further enrollment and study treatment will be halted until a thorough review has been conducted by the Medical Monitor, PI for the trial, and the DSMB.

- If any SAE (or potentially life-threatening AE) or death verified as related to study treatment occurs, further enrollment and study treatment will be halted until a thorough review has been conducted by the Medical Monitor, PI for the trial, IRB (if applicable) and the DSMB.
- If three or more subjects in this study experience the same Grade 3 or 4 unexpected adverse event, verified per protocol definition and assessed as related to study treatment, further enrollment and study treatment will be halted until a thorough review has been conducted by the Medical Monitor, PI for the trial, and the DSMB.
- In the event of two identical, unexpected, Grade 4 toxicities, verified per protocol definition and assessed as related to study treatment, further enrollment and study treatment will be halted until a thorough review has been conducted by the Medical Monitor, PI for the trial, IRB (if applicable) and the DSMB.

The sponsor or designee will notify all Investigators and IRBs/EC (if required) regarding the outcome of any investigation stemming from a Study Pause.

### **3.4 IMMUNOGENICITY ASSESSMENT**

The study explores humoral and cell mediated immune responses to VGX-3100 in blood samples taken at baseline (i.e., Screening and Day 0 prior to dosing) and Weeks 15, 27, 48, 74 and 96. Vulvar samples will also be analyzed for evidence of immune responses at Screening and Weeks 48, 74 and 96. Samples will not be obtained at Week 96 for subjects who complete the study prior to this timepoint, per Amendment 5.0.

### **3.5 VIROLOGIC ASSESSMENT**

Tissue samples will be obtained to characterize vulvar HPV infection at Screening, Weeks 48, 74 and 96. Cervical samples, oropharyngeal (OP) rinse samples, vulvar, vaginal, and intra-anal tissue swab samples will be obtained to characterize HPV infection at the following time points: Day 0 prior to dosing (OP, cervical, vulvar, vaginal and intra-anal), Week 4 (Vulvar only), Week 12 (Cervical and Vulvar) and Weeks 27, 48, 74 and 96 (OP, vulvar, vaginal and intra-anal only). Samples will not be obtained at Week 96 for subjects who complete the study prior to this timepoint, per Amendment 5.0. At week 48 and 96, a cervical sample will also be collected.

## **4. SELECTION OF SUBJECTS**

### **4.1 INCLUSION CRITERIA**

Each subject must meet all of the following criteria to be enrolled in the study:

1. Must understand, agree and be able to comply with the requirements of the protocol. Subjects must be willing and able to provide voluntary consent to participate and sign a Consent Form prior to study-related activities;
2. Women aged 18 and above;
3. Vulvar infection with HPV types 16 and/or 18 confirmed by screening biopsy;
4. Vulvar tissue specimen/blocks must be collected within 10 weeks prior to anticipated date of first dose of study drug and have confirmed histologically confirmed vulvar HSIL by the Pathology Adjudication Committee at screening;

5. Must be judged by the Investigator to be an appropriate candidate for the protocol-specified procedure (i.e. excision or biopsy) required at Week 48;
6. Must have vulvar HSIL that is accessible for sampling by biopsy instrument and of adequate size to ensure that a visible lesion remains after an approximately 4 mm screening biopsy;
7. Must have vulvar HSIL that can be completely demarcated for area measurement;
8. Must meet one of the following criteria with respect to their reproductive capacity:
  - a. Is post-menopausal as defined by spontaneous amenorrhea for more than 12 months or spontaneous amenorrhea for 6-12 months with FSH level >40 mIU/mL;
  - b. Is surgically sterile due to absence of ovaries or due to a bilateral tubal ligation/occlusion performed more than 3 months prior to screening;
  - c. Women of Child Bearing Potential (WOCBP) are willing to use a contraceptive method with failure rate of less than 1% per year when used consistently and correctly from screening until 6 months following the last dose of investigational product. Acceptable methods are the following:
    - i. Hormonal contraception: either combined or progestin-alone including oral contraceptives, injectable, implants, vaginal ring, or percutaneous patches. Hormonal contraceptives must not be used in subjects with a history of hypercoagulability (e.g., deep vein thrombosis, pulmonary embolism);
    - ii. Abstinence from penile-vaginal intercourse when this is the subject's preferred and usual lifestyle;
    - iii. Intrauterine device or intrauterine system;
    - iv. Male partner sterilization at least 6 months prior to the female subject's entry into the study, and this male is the sole partner for that subject.
9. Normal screening electrocardiogram (ECG) or screening ECG with no clinically significant findings as judged by the Investigator.

## 4.2 EXCLUSION CRITERIA

Subjects meeting any of the following criteria will be excluded from the study:

1. Untreated microinvasive or invasive cancer;
2. Biopsy-proven Vaginal Intraepithelial Neoplasia (VAIN) and are not undergoing medical care and/or treatment for VAIN;
3. Biopsy-proven Anal Intraepithelial Neoplasia (AIN) and are not undergoing medical care and/or treatment for AIN;
4. Biopsy-proven Cervical Intraepithelial Neoplasia (CIN) 2/3 and are not undergoing medical care and/or treatment for CIN;
5. Biopsy-proven differentiated VIN;
6. Vulvar HSIL that is not accessible for sampling by biopsy instrument;
7. Vulvar HSIL that is not of adequate size to ensure that a visible lesion remains after biopsy;

8. Treatment for genital warts within 4 weeks prior to screening;
9. Any previous treatment for vulvar HSIL (e.g. with surgery and/or imiquimod) within 4 weeks prior to screening;
10. Allergy to imiquimod 5% cream or to an inactive ingredient in imiquimod 5% cream for subjects enrolled prior to Protocol Amendment v3.0 (dated 26Mar2019);
11. Is pregnant, breastfeeding or considering becoming pregnant within 6 months following the last dose of investigational product;
12. Presence of any unresolved abnormal clinical laboratory values greater than Grade 1 per Common Terminology Criteria for Adverse Events (CTCAE) v 4.03 within 45 days prior to Day 0 or less than or equal to Grade 1 but deemed clinically significant by the Investigator;
13. Immunosuppression as a result of underlying illness or treatment including:
  - a) History of or positive serologic test for HIV at screening;
  - b) Primary immunodeficiencies;
  - c) Long term use ( $\geq 7$  days) of oral or parenteral glucocorticoids at a dose of  $\geq 20$  mg/day of prednisone equivalent (use of inhaled, nasal, otic, and ophthalmic corticosteroids are allowed);
  - d) Current or anticipated use of disease modifying doses of anti-rheumatic drugs (e.g., azathioprine, cyclophosphamide, cyclosporine, methotrexate) and biologic disease modifying drugs such as TNF- $\alpha$  inhibitors (e.g. infliximab, adalimumab or etanercept);
  - e) History of solid organ or bone marrow transplantation;
  - f) Any prior history of other clinically significant immunosuppressive or clinically diagnosed autoimmune disease that may jeopardize the safety of the subject or require therapy that would interfere with study assessments or endpoint evaluation, or otherwise impact the validity of the study results.
14. History of previous therapeutic HPV vaccination (licensed prophylactic HPV vaccines are allowed, e.g. Gardasil®, Cervarix®);
15. Received any non-study related non-live vaccine within 2 weeks of each study dose;
16. Received any non-study related live vaccine (e.g. measles vaccine) within 4 weeks of each study dose;
17. Significant acute or chronic medical illness that could be negatively impacted by the electroporation treatment as deemed by the Investigator;
18. Current or history of clinically significant, medically unstable disease which, in the judgment of the Investigator, would jeopardize the safety of the subject, interfere with study assessments or endpoint evaluation, or otherwise impact the validity of the study results
  - a) Chronic renal failure, angina, myocardial ischemia or infarction, class 3 or higher congestive heart failure, cardiomyopathy, or clinically significant arrhythmias;
  - b) Treatment for non-anogenital malignancy within 2 years of screening, with the exception of superficial skin cancers that only require local excision;
  - c) Bleeding or clotting disorder or use of blood thinners (e.g. anticoagulants or antiplatelet drugs) that would contraindicate IM injections within 2 weeks of Day

- 0;
  - d) History of seizures unless seizure free for 5 years with the use of one or fewer antiepileptic agents;
  - e) Sustained, manually confirmed, sitting systolic blood pressure >150 mm Hg or <90 mm Hg or a diastolic blood pressure >95 mm Hg at Screening or Day 0;
  - f) Resting heart rate <50 bpm (unless attributable to athletic conditioning) or >100 bpm at Screening or Day 0;
  - g) Prior major surgery within 4 weeks of Day 0;
19. Participated in an interventional study with an investigational compound or device within 4 weeks of signing informed consent (participation in an observational study is permitted);
20. Less than two acceptable sites available for IM injection considering the deltoid and anterolateral quadriceps muscles;
- a) Tattoos, keloids or hypertrophic scars located within 2 cm of intended treatment site;
  - b) Cardioverter-defibrillator or pacemaker (to prevent a life-threatening arrhythmia) (unless deemed acceptable by a cardiologist);
  - c) Metal implants or implantable medical device within the intended treatment site (i.e. electroporation area);
21. Vulnerable populations:
- a) Active drug or alcohol use or dependence that, in the opinion of the Investigator, would interfere with adherence to study requirements;
  - b) Prisoner or subject who is compulsorily detained (involuntarily incarcerated) for treatment of either a psychiatric or physical (i.e. infectious disease) illness;
  - c) Active military service personnel who have the potential to be relocated;
  - d) Study-related staff or family members of study-related staff;
22. Any illness or condition that in the opinion of the Investigator may affect the safety of the subject or the evaluation of any study endpoint.

